Corticotropin-releasing hormone (CRH) is a principal regulator of the hypothalamic-pituitary-adrenal axis. CRH is released from the placenta and fetal membranes during pregnancy. Plasma CRH levels observed during labor peak during vaginal delivery (serum levels ranging from 2 to 3000 pmol/liter during labor) (6, 8, 9). The CRH functions as the “surveillance and response” for the placental. This allows the fetus to detect threats to survival, and if viable, the fetus can adjust its developmental course. In 2007, O'Sullivan et al. reported that congenital adrenal hyperplasia in the fetus is associated with 21-hydroxylase deficiency. In addition, a late gestational rise may lead to impaired cortisol production by the fetal adrenal gland (10).

Studies by Mohaghegh et al. and Latif et al. demonstrated that glucocorticoids like dexamethasone play a pivotal role in cervical ripening and aid labor induction (2, 8). Prior studies have used dexamethasone as the chosen glucocorticoid to investigate its role in labor induction. The effect

of dexamethasone on the interval length at the beginning of labor induction has been explored, as its effects at the beginning of the active phase of labor. (3, 8, 11-14). However, there is a paucity of studies because of the high heterogeneity among pregnant women. There is a need for double-blind clinical trials to solidify the use of dexamethasone for improving cervical Bishop scores in pregnant women. As outlined, the role of corticosteroids in labor induction remains unclear. The effect of using corticosteroids vaginally for labor induction requires further investigations. Therefore, we undertook a triple-blinded randomized controlled trial (RCT) where dexamethasone was the chosen glucocorticoid used for labor induction. This study aimed to examine the effect of using dexamethasone administered vaginally and whether it can enhance the Bishop score and reduce the duration of the latent phase of labor in nulliparous pregnant women.

Methods

Study design

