This was a triple-blinded randomized controlled trial conducted in Kamali Hospital, Karaj, Iran. Kamali Hospital is one of the teaching hospital subsets at Alborz University of Medical Sciences. Ethical approval was ceded to the ethical committee of Alborz university. The ethics committee approved the study protocol. The RCT was conducted between October 2019 and June 2021. It was registered as an RCT with the following ID number: IR. ABZUMS. REC1399.067. Additionally, it was registered on clinicaltrial.gov, NCT05070468.

A sufficient sample size is required to compare the mean of the two groups (15). Using a 95% confidence interval and power of 90%, it was estimated that at least 84 participants were required. The participants were randomly divided into two groups of 42 as either cases or controls. The statistician assigned the participants to two groups using a balanced block randomization method using allocation into quadruple blocks. There were six modes for each case, two participants were in the control group, and two were in the intervention group. Thus, the participants were selected using the table of random numbers and assigned the numbers one to six within the groups of four.

Objectives

The clinical trial investigators and researcher staff were involved in all aspects of the study design and administration of the RCT. This included screening pregnant patients to assess if they met the

study inclusion criteria. These criteria required being a nulliparous Iranian woman pregnant, having full-term gestation (≥ 38 weeks), with a singleton pregnancy, between 18 to 35 years of age, and having normal Body Mass Indices (BMI) of 18.5—24.9. Labor induction was started in the participants when the membranes ruptured without the initiation of labor. The fetus was required to be in cephalic presentation, as shown on an ultrasound; there was a Bishop score of ≤ 2 and an estimated fetal weight of 2500-4000 grams. Participants were expected to have had normal Non-Stress Test (NST) results. If the patient's obstetric physician indicated termination of pregnancy, they could be eligible and randomized into case and control groups by a statistician.

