Exclusion criteria required the pregnant woman not to take any hormones or herbal medicines (traditional medicines), herbal/natural products, or conventional/prescribed medications during her pregnancy. Those who had the following pre-existing diseases, including diabetes mellitus, hypertension, a history of obstetric complications such as preeclampsia or eclampsia, or HELLP (Hemolysis, Elevated Liver enzymes, and Low Platelets) syndrome, were excluded. If the pregnant individual had previously presented with fetal immobility/decelerations or a history of maternal bleeding, they could not be enrolled in the clinical trial.

To enroll eligible patients, the investigator explained the study to potential participants and asked them to consider being in the study after considering all the presented information. Written consent was obtained from all recruited patients. Once enrolled, the patients, investigators, and research staff were blinded to which groups the participants were allocated. Dexamethasone and placebo tablets were labeled Tablets A and B and delivered by the hospital pharmacist. The research staff was blinded to which tablets were the study drug. The study design required that the tablets be administered vaginally by the obstetrician. Fourteen dexamethasone tablets (0.5 mg) were administered in group A, and 14 placebo tablets were given in the same manner to the participants in group B.

Data collection

Data was collected using several tools, including interviews, observations, and a vaginal examination. The research staff designed a 2-page questionnaire which was used, and this included demographic information, i.e., current age, education, job, gravidity, parity, past medical history,

and BMI. The first and second Bishop scores, the latent phase duration, and delivery and intervention type were also recorded for each participant. The collected information was initially collected on paper forms.

Clinical intervention phase

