During the intervention phase, the modified Bishop score was assessed; this comprised a physical examination that evaluated the cervical length, consistency, dilation and position, and fetal head station. Per the study protocol, an obstetrician placed fourteen tablets (either Tablets A or B) within the vagina during labor. The fetal heart rate was closely monitored, and any changes in the Bishop score within 6 hours were recorded. During this time, an obstetric physician undertook the labor induction for the study participants.

There were three types of interventions used. The first was when the pregnant woman did not require to be induced. These individuals had effective and robust contractions during labor. Therefore, further induction of uterine contractions was not performed, and labor took its natural course. Second, labor was induced when the pregnant woman did not have strong enough or effective uterine contractions. In these situations, Oxytocin was administered to aid in the induction if the patient had a Bishop score of five or more. Third, during labor induction in those participants assigned to the cases group, Misoprostol was administered if they had a Bishop score of less than 5. Once proper cervix ripening had been achieved, this indicated the termination of Misoprostol's effects. Labor induction continued with oxytocin until uterine contractions were satisfactory and strong. At each stage, from initial enrollment into the study, the onset of labor symptoms, and until the end of the latent phase of labor (4 cm dilation), the research staff followed and evaluated the individual women every 30 minutes. To further increase the reliability of the examination results, the patient's cervical dilation was established by two separate examiners to verify the result of the vaginal examinations.

Statistical analysis

The statistical analysis collected data from reviewing the participant questionnaires. This was converted for analysis using the SPSS statistical software version 25.0 (IBM Corporation, Chicago, IL, USA). A chi-squared test was used to assess any statistical hypotheses. Qualitative variables

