were reported as percentages and frequency. Through the evaluation of data, the findings were evaluated by using the Kolmogorov-Smirnov and Shapiro-Wilk tests. Additional parametric and nonparametric analyses were performed. The subsequent assessment used the Mann-Whitney or T-Test (depending on the case). A p-value of ($P \leq 0.05$) was considered statistically significant in this study.

1. References:

1. Tenore JL. Methods for cervical ripening and induction of labor. *American family physician*. 2003;67(10):2123-8.

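### The Bishop-score comparison is unadjusted, its outcome (second score or change) is not named, and the recorded first score is not used; adjusting for it would be a modest, cheap improvement

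*Combined protocol and SAP*

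**What the plan says.** The last paragraph before Methods gives two aims for vaginal dexamethasone: "whether it can enhance the Bishop score and reduce the duration of the latent phase of labor". Under Data collection, "The first and second Bishop scores, the latent phase duration, and delivery and intervention type were also recorded for each participant". Under Clinical intervention phase, "any changes in the Bishop score within 6 hours were recorded". Under Objectives, entry requires that "there was a Bishop score of ≤ 2".

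The Statistical analysis section names a chi-squared test and two normality tests (Kolmogorov-Smirnov and Shapiro-Wilk). For numeric outcomes it then says: "The subsequent assessment used the Mann-Whitney or T-Test (depending on the case"). It also mentions further parametric and nonparametric analyses, without giving a method, outcome or covariate for them.

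On size, Study design says "A sufficient sample size is required to compare the mean of the two groups (15"), and then "Using a 95% confidence interval and power of 90%, it was estimated that at least 84 participants were required", divided 42 and 42. It gives no outcome variable, difference or SD.

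**The concern.** The title outcome can be read in two ways, as the second score or as the change from first to second. The text supports both and chooses neither. Tested without adjustment, the two have different precision, and which is better depends on rho, which the documents do not give. The first score is already recorded for every woman, and the named tests leave it out.

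Two things are at stake. A reader cannot tell which Bishop comparison was planned. Some precision may also be given up, little or more depending on rho.

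**Working it through.** **Inputs from the documents.** 42 per arm, 90% power, 5% significance level (taken as two-sided; sidedness is not stated), first score capped at 2.

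**Inputs assumed.** Rho from 0 to 0.5; a 1-point effect; second-score SD 1.5 (range 1.25 to 2.0); first score uniform on 0, 1, 2, so SD = sqrt(2/3) = 0.816.

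**The plan's own figure.** N = 84 cannot be reproduced, because no difference or SD is given. It can only be solved backwards. The normal approximation gives d = (1.960 + 1.282) x sqrt(2/42) = 0.707; the noncentral t gives d = 0.716. *If* 84 was sized on the second Bishop score, adjustment multiplies d by 1/sqrt(1 - rho^2), with 81 df. Power then rises from 90% to 90.3, 91.1, 92.5, 94.3 and 96.3% at rho 0.1, 0.2, 0.3, 0.4 and 0.5.

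**Second score against change.** With k = SD_first/SD_second, Var(change)/Var(second) = 1 + k^2 - 2 x rho x k. The change is therefore the less precise of the two when rho < k/2. The simulated SDs (0.816 and 1.52 after rounding) give 0.816/(2 x 1.52) = 0.27.

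**Simulation.** 40,000 replicates, 1-point effect, normal errors, second score rounded and limited to 0-13, SD before rounding held at 1.5 for every rho. Power in %:

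| rho | second score | change | ANCOVA | ANCOVA minus second | change minus second | ANCOVA 95% CI width |
|---|---|---|---|---|---|---|
| 0 | 83.9 | 73.9 | 83.5 | -0.4 | -10.0 | 1.33 |
| 0.1 | 84.3 | 78.0 | 84.3 | 0.0 | -6.3 | 1.32 |
| 0.2 | 84.3 | 81.6 | 85.3 | +1.0 | -2.7 | 1.30 |
| 0.3 | 84.0 | 85.0 | 86.6 | +2.6 | +1.0 | 1.27 |
| 0.4 | 84.6 | 89.2 | 89.5 | +4.9 | +4.6 | 1.22 |
| 0.5 | 84.3 | 92.3 | 92.1 | +7.8 | +8.0 | 1.16 |

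The unadjusted second score has a CI width of 1.32 at every rho. ANCOVA rejects in 5.0 to 5.1% of null trials. The second-score and change tests reach different verdicts in 10 to 14% of trials with an effect, and in 4.5 to 5.1% without one.

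**Range over SD (formula, no rounding).** At SD 1.25, 1.5, 1.75 and 2.0:
- second score: 95.2, 85.5, 73.5, 62.0%
- ANCOVA at rho 0.3: 96.7, 88.6, 77.4, 66.0%
- change at rho 0: 85.9, 75.6, 65.0, 55.4%

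**Against Mann-Whitney, the plan's other test.** 3,000 replicates, same effect and SD, assumed control mean 3, Mann-Whitney v linear ANCOVA:
- Moderate right skew (gamma shape 4): 87.3 v 82.6% at rho 0; 86.8 v 86.6% at rho 0.3.
- Strong right skew (gamma shape 1): 98.6 v 85.5% at rho 0; 94.3 v 86.3% at rho 0.3.
- Normal errors: ANCOVA leads by about 1 to 4 points over rho 0 to 0.3.

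A rank-based ANCOVA roughly matches or beats Mann-Whitney in every setting run. The form of the adjustment therefore has to follow the distribution.

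**The case against.** The strongest case against is that two matters are being joined. Naming the outcome takes one sentence. Adjusting for the first score is then a preference for precision, since randomisation already makes the unadjusted test valid. The entry cap narrows the first score, so rho may well be low, and the gain is then about a point or nothing. No figure above rests on an SD, effect or correlation from the documents. Linear ANCOVA can also lose clearly to Mann-Whitney on skewed scores. The trial is over ("The RCT was conducted between October 2019 and June 2021") and the document is dated 01/09/2021, so an adjusted analysis may be post hoc.

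All of this stands, and it limits the point to a modest one. It does not remove it. A low rho is where an unadjusted change score costs most, and the plan leaves that choice open. In linear ANCOVA the test of group is the same for the second score and the change once the first score is a covariate, so adjustment also settles that ambiguity.

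A reader might infer more than the documents support:
- **That the planned test is wrong.** It is not; an unadjusted second-score test is valid.
- **That the false-positive rate was inflated.** If both quantities were tested and either counted as success, the null disagreement above would imply (5 + 5 + 4.5)/2 to (5 + 5 + 5.1)/2, about 7.3 to 7.6%. Nothing says this was done. Assuming equal SDs gives 8.3 to 9.4%, and also 63% change-score power at rho 0, but the cap at 2 makes equal SDs doubtful.
- **That no adjusted analysis was done.** The unspecified further analyses mean only that none is named.

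**Conclusion.** The point holds as a modest improvement. The text does not define the Bishop comparison and names no use of the first score. Under the base assumptions, adjustment adds about 0 to 1 power point for rho up to 0.2 and about 5 at rho 0.4. The 10-point loss requires both an unadjusted change score and rho near 0; at rho 0.2 it is 2.7 points, and from 0.3 the change is the better unadjusted test. The textual gap depends on none of the assumed inputs, but the size of the benefit depends on all of them. The calculation from d = 0.716 further assumes that 84 was sized on the second Bishop score, although latent-phase duration is the other stated aim.

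**What to change.** In the Statistical analysis section:

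1. Name the second Bishop score as the Bishop outcome and state when it was taken, reconciled with the 6-hour window under Clinical intervention phase.
2. Compare groups with the first score as covariate. If the scores are roughly normal, use ANCOVA and report the adjusted mean difference with its 95% CI. Where the plan would have used Mann-Whitney, make a rank-based ANCOVA or a proportional-odds model with the same covariate the main analysis.
3. Show the unadjusted second-score result beside it.
4. Label the adjusted analysis as not pre-specified if the data had been seen.

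The cost is a few sentences and no new data. The downsides are up to about 0.5 power points lost if rho is near 0, and little gain if rho is low.
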